#### 3.3.1.3 Nights with awakening due to asthma

Bi-weekly mean number (expressed as percentage) of nights with awakening due to asthma that required rescue medication will be calculated as the outcome variable. The bi-weekly mean number (percentage) calculation for Week 12 (Visit 9) will include the night-time entries on 14 sequential days up to and including the entries on the morning of the Week 12 (Visit 9) visit.

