## 5.1.12 Assessment of asthma exacerbation

Assessment of asthma exacerbation will be performed in accordance with the schedule provided in Table 1.

For the purpose of the study, an asthma exacerbation will be defined as a worsening of asthma that leads to any of the following:

- A temporary bolus/burst of systemic corticosteroids for at least 3 days to treat symptoms of asthma worsening; a single depo-injectable dose of corticosteroids will be considered equivalent to a 3-day bolus/burst of systemic corticosteroids
- An emergency room or urgent care visit (defined as evaluation and treatment for <24 hours in an emergency department or urgent care centre) due to asthma that required systemic corticosteroids (as per the above)
- An in-patient hospitalization (defined as admission to an inpatient facility and/or evaluation and treatment in a healthcare facility for ≥ 24 hours) due to asthma

Worsening of asthma is defined as new or increased symptoms and/or signs (examination or lung function) that can be either concerning to the subject (subject-driven) or related to an asthma daily diary alert (diary-driven). Baseline values for diary-driven alerts will be the mean of measures collected between Visits 1 and 2.

The eDiary will be programmed to alert both the subject and study centre when certain prespecified worsening thresholds are crossed including:

- Decrease in morning peak flow ≥20% on at least 2 consecutive days compared with baseline, and/or
- An increase in rescue medication use of 4 or more puffs, or use of one new or additional nebulized  $\beta 2$  agonist on at least 2 consecutive days compared with the average use during baseline, and/or

- An increase of 2 nocturnal awakenings due to asthma over a 7 day period compared with the average during baseline, and/or
- An increase in total asthma symptom score (the sum of day time [evening assessment] and night time [morning assessment] of at least 2 units above the baseline average or the highest possible score (daily score of 6), on at least 2 consecutive days

If an exacerbation event is not associated with deterioration in at least 1 of the pre-specified objective measurements, the Investigator will have to justify the decision for defining the event as an exacerbation and record it in the eCRF. Events that are not supported by any objective assessment will be deemed not to be a protocol-defined exacerbation.

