#### **Rescue medication**

The number of rescue medication inhalations (puffs) and nebulizer treatments taken will be recorded by the subject in the Asthma Daily Diary twice daily (i.e., in the morning and evening) beginning the evening of Visit 1 until the morning of Visit 9. The number of inhalations taken between the morning and evening lung function assessments will be recorded in the evening. The number of inhalations taken between the evening and the morning will be recorded in the morning.

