#### Nocturnal awakenings

Nocturnal awakenings due to asthma symptoms will be recorded by the subject in the Asthma Daily Diary each morning, beginning in the morning after Visit 1 until the morning of Visit 9, by answering question whether he/she woke up during the night due to asthma symptoms by a "yes" or "no" response.

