#### 8.4.4.4 Effect on asthma symptoms and other asthma control metrics

For asthma symptom score, rescue medication use and home PEF, biweekly means will be calculated. A biweekly mean is calculated as the sum of all non-missing daily measures/scores over 14 sequential days divided by the number of non-missing daily measures/scores. For nights with awakenings due to asthma, the bi-weekly mean will be the percentage of times the subject answered "yes" to 'did your asthma cause you to wake up' and "yes" to 'did you use rescue medication upon awakening'. If more than 7 daily measures/scores (>50%) within a period is missing, then the bi-weekly mean for that period is set to 'missing'.

Percent change from baseline will be calculated as described in Section 8.4.1.

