#### Nights with awakening due to asthma

The total biweekly number of nights with awakening due to asthma that required rescue medication will be calculated as the outcome variable.

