	
 
Morphometry parameters (lumen area [LA], wall area [WA] and wall area %) for airway generations 3, 4 and 5 (segmental, sub-segmental, sub-segmental),
 
Airway resistance for airway generations 3, 4 and 5 estimated based on lumen area,
 
Airway volume and resistance for entire airway tree (lobar or lung level) based on Functional Respiratory Imaging (FRI) (Optional)
 
	

Exploratory Objectives:	Outcome Measures:
Exploratory Objectives: To evaluate the effect of tralokinumab on small airways remodelling in adult subjects with asthma inadequately controlled with ICS	
 
Outcome Measures:
 
Change from baseline up to Week 12 in
 
R5-R20 and AX as evaluated by Impulse Oscillometry (IO),
 
Sacin (Index of acinar ventilation heterogeneity) by using multiple breath washout (MBW),
 
Air trapping expressed as percentage of the lung with expiratory density less than -856 HU, and as expiratory-to-inspiratory ratio of mean lung density on CT,
 

	
 
Regional matching of the inspiratory/expiratory CT scans to assess air trapping/small airway obstruction,
 
Extent of gas trapping determined from physiologic testing by total lung capacity (TLC)/ residual volume (RV)/ vital capacity (VC)/inspiratory capacity (IC)/functional residual capacity (FRC)
 

To evaluate the effect of tralokinumab on asthma symptoms and other asthma control metrics in adult subjects with asthma inadequately controlled with ICS	
 
Change from baseline up to Week 12 in
 
Daily asthma symptom scores (combined daytime and night-time score)
 
Rescue medication use
 
Home peak expiratory flow (PEF) (morning and evening)
 
Number of night-time awakening due to asthma
 
Asthma Control Questionnaire 6 (ACQ-6)
 

Exploratory Objectives:	Outcome Measures:
To evaluate the effect of tralokinumab on lung function and bronchial hyper- responsiveness in adult subjects with	Change from baseline up to Week 12 in pre BD (Bronchodilator) and post BD spirometry
asthma inadequately controlled with ICS	- Forced expiratory volume in 1 second (FEV 1 ),
	- Forced vital capacity (FVC),
	
 
Forced expiratory flow between 25% and 75% of the forced vital capacity (FEF25-75%),
 

	Change from baseline up to Week 12 in
	- Airway Hyper-responsiveness (AHR).

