### 4.2.8.3 Nights with awakening due to asthma

The change from baseline in the bi-weekly mean number (percentage) of nights with awakening due to asthma that required rescue medication will be summarized as described in Section 4.2.5.1 for the descriptive statistics only – there won't be any MMRM.

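### The stated exploratory measure is night-time awakening due to asthma, but the only derived diary variable counts nights with awakening that also required rescue medication, and no summary of nights with any awakening is planned

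*SAP*

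**What the plan says.** The objectives tables (protocol 2.4, SAP 1.1.4) list the measure as "Number of night-time awakening due to asthma". Rescue use is a separate entry in the same list.

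The derived variable adds a condition. Protocol 8.4.4.4, under the heading on nights with awakening, has "The total biweekly number of nights with awakening due to asthma that required rescue medication will be calculated as the outcome variable". SAP 3.3.1.3 has "Bi-weekly mean number (expressed as percentage) of nights with awakening due to asthma that required rescue medication will be calculated as the outcome variable". SAP 4.2.8.3 carries it into the analysis: "The change from baseline in the bi-weekly mean number (percentage) of nights with awakening due to asthma that required rescue medication will be summarized", by descriptive statistics only. The general paragraphs of protocol 8.4.4.4 and SAP 3.3 make the rule explicit. A night counts only if the subject says yes to having been woken by asthma and also yes to a second item, "did you use rescue medication upon awakening".

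On data collection, the Nocturnal awakenings paragraph of protocol 5.3.2.1 describes one item, answered yes or no each morning: the subject reports "by answering question whether he/she woke up during the night due to asthma symptoms". The Rescue medication paragraph of the same section says "The number of inhalations taken between the evening and the morning will be recorded in the morning".

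**The concern.** The measure and its headings speak of awakening due to asthma. The variable measures awakening that led to rescue use. A night on which the subject woke and took nothing contributes zero, exactly as an undisturbed night does. A reader who goes from the objective to a table headed nights with awakening would take the figures for something they are not.

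The variable also joins two things, waking and what the subject does on waking. Rescue use already has its own outcome variable, so a change in rescue habit alone could move this one while waking stayed the same. What is at stake is whether the trial reports its stated exploratory measure at all, given that the item needed for it is collected daily.

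**Working it through.** The plan gives no figure to reproduce, so the check is a comparison of the texts, followed by a small illustration.

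**Texts side by side**

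- Stated measure (protocol 2.4, SAP 1.1.4): awakening due to asthma, no rescue condition.
- Diary item (protocol 5.3.2.1): woke because of asthma, yes or no, each morning. This supports a percentage of nights with any awakening. It cannot count several awakenings within one night.
- Derived variable (protocol 8.4.4.4; SAP 3.3, 3.3.1.3, 4.2.8.3): yes to waking and yes to rescue on waking.
- Declared changes (SAP section 6): for this variable, only the move from a number to a percentage. The rescue condition is not listed because the protocol already has it.

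**Does another planned summary supply the stated measure?**

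- ACQ-6 includes an item on being woken at night, and SAP 4.2.8.2 summarises the individual questions. That item is a 0 to 6 rating recalled over the previous week and taken at selected visits. It does not count nights.
- The night-time symptom score (SAP 3.3.1.1) is a 0 to 3 rating of symptoms and does not record waking.
- All data are to be listed (SAP 4.1), but a listing is not a summary by treatment.

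So no planned summary gives nights with any awakening.

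**Illustration, with assumed counts.** Let N be the nights with diary data in the two-week period, A the nights with any awakening, and R the nights with awakening and rescue, so that R is at most A. The percentage of nights with any awakening is 100 × A/N; the derived variable is 100 × R/N. Take N = 14 and A = 6, so that any awakening is 6/14 = 42.9%.

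- R = 6: the derived variable is 6/14 = 42.9%.
- R = 3: 3/14 = 21.4%.
- R = 0: 0%.

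Now compare changes from baseline on the two measures, again with assumed counts.

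- A stays at 6 and R goes from 3 to 0: no change in waking; the derived variable falls from 21.4% to 0%.
- A goes from 6 to 3 and R stays at 3: waking falls from 42.9% to 21.4%; the derived variable stays at 21.4%.
- A goes from 6 to 3 and R from 6 to 0: waking falls from 42.9% to 21.4%; the derived variable falls from 42.9% to 0%.

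The derived variable can therefore show a change where waking has none, miss a change in waking, or show a larger one. Which of these would apply here depends on R/A by arm and visit, and neither document gives that.

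**The case against.** The best defence is that the definition is deliberate, prespecified and the same in both documents. An objectives table gives short labels; the derivation section defines the variable, and its own sentence says plainly that rescue was required. Awakening that needed rescue is a reasonable severity threshold, and preferring any awakening is partly taste. The diary alert, "An increase of 2 nocturnal awakenings due to asthma over a 7 day period", carries no rescue condition, but an alert that prompts evaluation need not match an outcome variable. All of this stands. It argues for keeping the variable. It does not explain why the measure named in the objectives goes unsummarised.

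Three stronger readings are tempting, and the documents support none of them.

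- A reader of the Nocturnal awakenings paragraph alone might infer that the rescue component is not collected and that the variable cannot be derived. Protocol 8.4.4.4 and SAP 3.3 both quote the second question, and night-time inhalations are recorded each morning. What remains is that protocol 5.3.2.1 does not list that question, and that the inhalation count is not tied to an awakening.
- A reader might infer that the SAP departed from the protocol. It did not; the restriction is in both.
- A reader might infer that the variable must dilute a treatment effect. If a constant share of awakenings led to rescue, say 0.3, 0.5 or 0.7 (assumed), a 10-point fall in nights with awakening would show as 10 × 0.3 = 3, 10 × 0.5 = 5 or 10 × 0.7 = 7 points. Even then the relative change would be the same. Nothing in the documents supports those shares or their constancy across arms and time. If treatment made awakenings milder, the derived variable could fall proportionally more than waking itself.

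**Conclusion.** The point holds as a mismatch between a stated measure and its only derived variable, present in protocol and SAP alike. Nights of waking without rescue are left out, and the measure as named is not summarised although the diary item for it exists. The size and direction of any consequence for the comparison of tralokinumab with placebo cannot be determined from the documents; the percentages in the illustration rest on assumed counts and show only that the two measures can diverge.

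The weight is small. The variable is exploratory and summarised descriptively with no MMRM; the sample size and the primary and secondary analyses do not depend on it. The conclusion assumes that the waking answer is stored as its own field, as protocol 5.3.2.1 describes, and that nights with any awakening is the closest available form of the stated measure, given a yes/no item.

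**What to change.** In SAP 3.3.1.3 and 4.2.8.3, add the bi-weekly percentage of nights with any awakening due to asthma, taken from the yes/no question in protocol 5.3.2.1, as the summary that matches the stated measure. Use the same 14-night window, baseline and missing-data rule as for the existing variable. Keep the existing variable unchanged and label it, in headings and tables, as nights with awakening due to asthma requiring rescue medication. State in the SAP that the second component comes from the rescue-on-awakening question, since protocol 5.3.2.1 does not list it.

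The cost is a few lines of SAP text, a relabelled table and one more descriptive row. No new data are needed.

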#### **3.3.1.4** Home peak expiratory flow (morning and evening)

Bi-weekly mean changes from baseline in morning (night-time) and evening (daytime) PEF will be calculated as the outcome variable. The Week 12 (Visit 9) bi-weekly mean daytime and night-time PEF will be as described for daytime and night-time asthma symptom scores in Section 3.3.1.1.

#### 3.3.1.5 Asthma Control Questionnaire (ACQ-6)

In the ACQ-6 questionnaire the subjects are asked to recall the status of their asthma during the previous week with regards to symptom and use of short acting  $\beta$ -agonists. The questionnaire include questions on

- 1. Awoken at night by symptoms
- 2. Limitation of normal daily activities
- 3. Waking in the morning with symptoms

- 4. Dyspnoea
- 5. Wheeze
- 6. Daily rescue medication

The questions of the ACQ-6 are measured on a 7-point scale scored from 0 (totally controlled) to 6 (severely uncontrolled). The ACQ-6 score is computed as the un-weighted mean of the responses to the 6 questions. If response to any of the questions is missing, the ACQ-6 score will be missing.

The outcome variable for the ACQ-6 will be the change in mean score from baseline to each of the post-randomization assessments. The change from baseline for each question will also be calculated.

Other variables based on ACQ-6 to report include:

- ACQ-6-responder (Yes=1/No=0)
  - Responder: Change from baseline ACQ-6 score  $\leq$  -0.5
  - $\circ$  Non-responder: Change from baseline ACQ-6 score > -0.5
- ACQ-6-response (Improved/No Change / Deterioration)
  - Improvement: Change from baseline ACQ-6 score  $\leq$  -0.5
  - $\circ$  No change: -0.5 < Change from baseline ACQ-6 score < 0.5
  - Deterioration: Change from baseline ACQ-6 score  $\geq 0.5$
- Subjects asthma control as measured by ACQ-6 score:
  - Well controlled : ACQ-6 score  $\leq 0.75$
  - $\circ$  Partly controlled: 0.75 < ACQ-6 score < 1.5
  - Not well controlled: ACQ-6 score  $\geq 1.5$

The ACQ-6-responder, the ACQ-6-response, and subject asthma control variables will be analysed only considering non-missing ACQ-6 values.

#### 3.3.1.6 Sino-Nasal Outcome Test - 20 (SNOT-20)

In the SNOT-20 the subjects are asked to recall their experiences during the previous 2 weeks and to score each of the 20 questions [divided across five subgroups 1) nasal symptoms, 2) paranasal symptoms, 3) sleep-related symptoms, 4) individual impairment 5) social impairment and emotional impairment] on a 6-point scale ranging from 0 (no problem) to 5

(most serious problem). In addition they are asked to record which of the five subgroups they consider to be the most important. The total score is calculated as the sum of the responses to all questions answered. There will be no imputation for missing data.

The outcome variable for the SNOT-20 will be the change in total score from baseline to Week 12 (Visit 9).

For each question and visit, the number and percentage of subjects who ticked the corresponding question as "most important" will be summarised.

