#### 8.4.4.5 Effect on rhinosinusitis symptom metrics

Using the SNOT-20 questionnaire, subjects are asked to recall their experiences during the previous 2 weeks and to score each of the 20 questions on a 6-point scale ranging from 0 (no problem) to 5 (problem as bad as it can get).

The total score is calculated for all the questions answered.

The main outcome variable for the SNOT-20 will be the change in total score from baseline to week 12. The change from baseline will be derived as post-randomization score minus baseline score, there will be no imputation for missing values.

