#### 3.1.2 Absolute and percent change from baseline

Absolute change from baseline outcome variables is computed as

(post-randomization value – baseline value).

Percent change from baseline is computed as

((post-randomization value – baseline value) / baseline value)  $\times$  100%.

Ratio of post-randomization value to baseline value is computed as

(post-randomization value / baseline value).

For the analysis of ratios, a log transformation is required. If either the post-randomization value or the baseline value is missing, then the absolute or percent change from baseline or the ratio value will also be set to missing.

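### The SNOT-20 sum rule counts a skipped item as 0, the best score, so an incomplete form can distort that subject's change score

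*SAP*

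**What the plan says.** SAP 3.3.1.6 gives the scoring rule: "The total score is calculated as the sum of the responses to all questions answered". It adds: "There will be no imputation for missing data". Protocol 8.4.4.5 is looser. It says "The total score is calculated for all the questions answered" without naming a sum and, in the sentence that derives the change from baseline, "there will be no imputation for missing values". It describes the instrument as "20 questions on a 6-point scale ranging from 0 (no problem) to 5", so a complete form totals between 0 and 100.

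The outcome is the change in total from baseline (Visit 3c) to Week 12 (Visit 9), the only two SNOT-20 assessments in protocol Table 1. Under SAP 3.1.2, if either value is missing, "then the absolute or percent change from baseline or the ratio value will also be set to missing". A partly answered form still has a total, so that clause does not catch it.

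The form is completed on paper at the site and transcribed into the eCRF (protocol 5.3.2.3). SAP Section 6 confirms that the data come from RAVE and not from the e-diary. Neither document gives a minimum number of answered items, a prorating rule, or a rule that voids an incomplete SNOT-20 total. For ACQ-6, by contrast, SAP 3.3.1.5 says: "If response to any of the questions is missing, the ACQ-6 score will be missing".

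**The concern.** Adding up only the answered items is arithmetically the same as entering 0 for each blank. On this scale 0 is the favourable end, so the rule acts as a best-case substitution on any incomplete form. The wording itself allows for unanswered questions, and no forced completion is described for the paper form.

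The SAP does not let a missing component count as zero in its other composite patient-reported scores. Besides ACQ-6, the daily asthma symptom total (SAP 3.3.1.1) and daily rescue use (SAP 3.3.1.2) are sums, and each is set to missing when its daytime or night-time part is absent.

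Change in SNOT-20 total is the only outcome listed for the rhinosinusitis objective, so a scoring error at either visit passes straight into the only result reported for it.

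**Working it through.** The documents state no figure for SNOT-20 scoring, so there is nothing to reproduce. The check applies the stated rule.

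**Inputs from the documents:** 20 items, each scored 0 to 5; total = sum of answered items; change = Week 12 total minus baseline total.

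**Assumptions, because the documents give no values:** item means of 1, 2 and 3; the number of items skipped; the share of subjects who skip. Skipped items are taken to be typical of the subject's other items.

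**1. Items skipped at one visit, stable subject.** With item mean m and k items skipped, the complete total is 20 × m and the scored total is (20 − k) × m. The false change is −k × m if the skip is at Week 12 and +k × m if it is at baseline.

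| Items skipped (k) | m = 1 | m = 2 | m = 3 |
|---|---|---|---|
| 1 | 1 | 2 | 3 |
| 2 | 2 | 4 | 6 |
| 5 | 5 | 10 | 15 |

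Entries are points of false change: negative for a Week 12 skip, positive for a baseline skip. For example, with m = 2 and four items skipped at Week 12, 20 × 2 = 40 becomes 16 × 2 = 32, a change of −8 with no change in symptoms. The exact error for one item equals its unrecorded answer, so it runs from 0 to 5 points.

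**2. Same items skipped at both visits.** A stable subject shows no false change, but a real change shrinks. If every item falls from 2 to 1, the true change is 20 × (1 − 2) = −20. With two items skipped at both visits it is 18 × (−1) = −18; with five, 15 × (−1) = −15.

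**3. Arm mean.** If a share p of an arm skips k items at Week 12 only, the arm mean change shifts by −p × k × m. Over assumed p of 5% to 20%, k of 1 to 4 and m of 1 to 3:
- smallest: 0.05 × 1 × 1 = 0.05, a shift of −0.05 points;
- largest: 0.20 × 4 × 3 = 2.4, a shift of −2.4 points on the 0 to 100 scale.

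**4. The same example under the alternatives.** Prorating gives 20 × (32 / 16) = 40, so the false change of −8 becomes 0. The ACQ-6 rule makes that subject's change missing.

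**The case against.** The strongest case on the other side is that little depends on this score.

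- **Status.** SNOT-20 is exploratory. Protocol 8.5.6 and SAP 4.2.6 provide descriptive statistics and graphs for exploratory variables. SAP 4.2.8.6 refers to Section 4.2.5.1 without repeating the descriptive-only restriction, but SAP Section 6 limits the MMRM to secondary efficacy. This stands, and it sets the severity.
- **Data queries.** Protocol 9.4 provides for queries on missing data and for source data verification, and the form is completed at the site. Some blanks may be recovered. An answer that the subject never gave may not be, so this is partial protection.
- **Blinding and randomization.** If skipping and item severity are similar in the two arms, the shifts largely cancel in the comparison and mainly add noise. This also stands. Each arm's own mean change would still be shifted when skips fall mostly at one visit.
- **ACQ-6 comparison.** ACQ-6 is a different instrument, scored as a mean and captured on the eDiary. A different rule for it is not a contradiction. It shows only that the SAP has a workable rule for incomplete forms.

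A reader might also infer that the plan contradicts itself by ruling out imputation while scoring blanks as 0. The documents do not make that clear-cut. The protocol never says sum, and its no-imputation clause is attached to the change from baseline, so it can be read as concerning absent visit totals.

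**Conclusion.** The point holds as a minor correction. The SAP rule gives a wrong total for an incomplete form whenever an unrecorded answer is above 0. On assumed item means of 1 to 3 the error in a subject's change is 1 to 3 points per item skipped at one visit, and it cannot exceed 5. Effects on arm means depend entirely on a skip rate that the documents do not give.

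A reader might go further and infer that every skipped item produces false improvement or worsening, or that the rule biases the treatment comparison. The documents support neither. Complete forms score correctly, a blank whose true answer was 0 causes no error, and items skipped at both visits attenuate real change instead of inventing it. Nothing in the documents suggests that skipping would differ between arms. Primary and secondary conclusions are unaffected.

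**What to change.** Replace the scoring sentence in SAP 3.3.1.6 with one of two rules:

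1. Total = 20 × the mean of answered items when at least 10 of the 20 are answered; otherwise missing. The one-half limit matches the one that the SAP already uses for bi-weekly diary means (Sections 3.1.1 and 3.3).
2. Total missing if any item is missing, as for ACQ-6.

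Prorating assumes that skipped items resemble answered ones, and it is itself a form of imputation, so the sentence excluding imputation would need rewording. The any-missing rule avoids that assumption but loses some subjects, possibly for one blank among 20 items. Either choice should be listed in SAP Section 6, where the SAP records departures from the protocol. The cost is one sentence in the SAP and one line of code, with no change to data collection.
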